6.1 Study treatment

6.1.1 Investigational drug

Dosing will be based on actual body weight and is administered IV via a syringe infusion pump.

For investigation: 6 mg/kg mavrilimumab will be infused on a pump.

For placebo: A similar infusion of the provided diluent will be used as placebo.

In preliminary experience with mavrilimumab in COVID-19, no infusion reactions have been reported, and pre-medication will not be required. In the event of an infusion reaction, the following interventions can be considered if needed: NaCl 0.9% IV infusion at 500 mL/hr, diphenhydramine 50 mg IV, hydrocortisone sodium succinate 100 mg IV, epinephrine 1mg/mL 0.3 mg intramuscular.

6.1.2 Additional study treatments

No additional treatment beyond investigational drug are included in this trial.

6.1.3 Treatment group

Eligible subjects will be assigned at the baseline visit to the treatment group in a consecutive fashion.

6.2 Other treatment(s)

6.2.1 Concomitant therapy

No formal drug-drug interaction studies have been conducted with mavrilimumab.

Medication classification used by the subject prior to randomization will be recorded in the eCRF pages.

Concomitant medications to track include: antipyretics, antibiotics related to secondary infections, and all investigational off-label therapies for COVID-19 for each subject (e.g. chloroquine, hydroxychloroquine, anti-IL-6, corticosteroids, remdesivir, lopinavir/ritonavir) along with time, dose, and duration of their administration. Other concomitant medications will be recorded at baseline and daily thereafter while patient is hospitalized until Day 7, at Day 14, Day 21 and Day 28. This information will be included in the final study report.

6.2.2 Prohibited medication

No data are available on either the effects of live vaccination or the secondary transmission of infection by live vaccines in patients receiving mavrilimumab. Therefore, live vaccines should not be given concurrently.

Treatment with cell-depleting biological therapies (e.g., anti-CD20), cell-depleting biological therapies (such as anti-tumor necrosis factor [TNF], anakinra, treatment with alkylating agents, treatment with cyclosporine A, azathioprine, cyclophosphamide, or mycophenolate mofetil (MMF). If a patient is on anti-Interleukin [IL]-6 [e.g. tocilizumab], or abatacept] prior to enrollment they are excluded, however it may be permitted after enrollment if the investigator deems it clinically necessary.

6.2.3 Subject numbering

Each subject is identified in the study by a Subject Number (Subject No.) based on central randomization, that is assigned when the patient is first enrolled for screening and is retained as the primary identifier for the subject throughout his/her entire participation in the trial. Upon

signing the informed consent form, the patient is assigned to the next sequential Subject No. available.

6.2.4 Treatment assignment, randomization

After meeting all inclusion/exclusion criteria and obtaining informed consent, patients will be randomized using a 1:1 allocation ratio to one of the two study arms. Randomization will be centralized through REDcap Cloud at C5 research at the Cleveland Clinic. Randomization will be stratified by site.

6.3 Treatment blinding

Subjects, investigator staff, persons performing the assessments, and the clinical trial team will be blinded to treatment. Only the Research Pharmacist and members of the Data Monitoring Committee will have access to the treatment assignments. If the clinical team decides that unblinding the patient is essential for subsequent significant clinical management, then the patient may be unblinded after discussion between the clinical team and the Principal Investigator.

6.4 Preparation and dispensation

Each study site will be supplied with study drug in packaging as described in the pharmacy manual.

A unique medication number is printed on the study medication label.

Each study site will be supplied with study drug and corresponding diluent/placebo. Clinical lots of KPL-301 drug product and corresponding diluent/placebo have been manufactured in different container formats; KPL-301: accessorized pre-filled syringes [APFS] and Diluent/Placebo: vials. The drug product is supplied with a diluent; the diluent will be used as the matching placebo. The deliverable or extractable volume for APFS and the vials is 1.0 mL, each. The Pharmacy Manual contains all the information about drug preparation.

APFS and vials are to be stored by the GMP pharmacy facility and investigator at 2-8 degrees Celsius at which temperature the product is viable until its listed expiry date.

Individual patient infusions are to be prepared at the investigational site under the authority of the investigator and in accordance with local regulations. Preparation of the investigational drug must be done in a separate space/room where study personnel have no access during time of preparation.

6.4.1 Handling of study treatment

6.4.1.1 Handling of study treatment

Study treatment must be received by a designated person at the study site, handled and stored safely and properly and kept in a secured location to which only the investigator and designated site personnel have access. Upon receipt, all study treatment must be stored according to the instructions specified on the labels and in the pharmacy manual. Clinical supplies are to be dispensed only in accordance with the protocol. Technical complaints are to be reported to the respective Kiniksa CPO Quality Assurance.

The investigator must maintain an accurate record of the shipment and dispensing of study treatment in a drug accountability log.

At the conclusion of the study, and as appropriate during the course of the study, the investigator will return all unused study treatment, packaging, drug labels, and a copy of the completed drug accountability log to the Kiniksa address provided in the investigator folder at each site.

7 Informed consent procedures

Eligible subjects may only be included in the study after providing (witnessed, where required by law or regulation), IRB -approved informed consent via site-approved procedures.

If applicable, in cases where the subject's representative(s) gives consent (if allowed according to local requirements), the subject must be informed about the study to the extent possible given his/her understanding. If the subject is capable of doing so, he/she must indicate agreement by personally signing and dating the written informed consent document.

Informed consent must be obtained before conducting any study-specific procedures (e.g. all of the procedures described in the protocol). The process of obtaining informed consent must be documented in the subject source documents.

Women of child bearing potential must be informed that taking the study treatment may involve unknown risks to the fetus if pregnancy were to occur during the study and agree that in order to participate in the study they must adhere to the contraception requirements.

A copy of the approved version of all consent forms will be kept by the Sponsor/Investigator.

7.1 Visit schedule and assessments

The assessment schedule lists all of the assessments and indicates with an “X”, the visits when they are performed. All data obtained from these assessments must be supported in the subject’s source documentation.

Subjects should be seen for all visits/assessments as outlined in the assessment schedule or as close to the designated day/time as possible. Missed or rescheduled visits should not lead to automatic discontinuation. Subjects who prematurely discontinue the study for any reason should be scheduled for a visit as soon as possible, at which time all of the assessments listed for the final visit will be performed.

Clinically significant abnormalities must be recorded on the relevant section of the CRFs capturing medical history/current medical conditions/AE as appropriate.

Table 7-1 Assessment Schedule^{tt}

Activity	Study Day ^a													Unscheduled ^d
	-3 to 0 ^b	0	1	2	3	4	5	6	7	14	21	28 ^c	60	
Informed consent	X													
Demographics	X													
Reason for hospitalization (COVID-19 pneumonia)	X													
Medical history	X													
Eligibility	X													
Physical exam	X													X
Vital signs	X	X	X	X	X	X	X	X	X	X	X	X	X	
Body Temperature (Celsius)	X	X	X	X	X	X	X	X	X	X	X	X	X	
Body weight	X													
Height	X													
Electrocardiogram	X													X
Chest imaging (CXR or chest CT)	X													X
Clinical assessment (6 category ordinal scale) ^a	X	X	X	X	X	X	X	X	X	X	X	X	X	
SOFA score	X								X	X	X	X	X	
2019-nCoV test*	X								X	X	X	X	X	
Respiratory Virus Panel	X													
CRP	X	X	X	X	X	X	X	X	X	X	X	X	X	
LDH ^e	X	X	X	X	X	X	X	X	X	X	X	X	X	
D-Dimer ^e	X	X	X	X	X	X	X	X	X	X	X	X	X	
Ferritin ^e	X	X	X	X	X	X	X	X	X	X	X	X	X	
Troponin	X													
NT-proBNP	X													
Mechanical ventilation assessment	X	X	X		X		X		X	X	X	X	X	
Respiratory parameters ^g	X	X	X		X		X		X	X	X	X	X	

Activity	Study Day ^a													
	-3 to 0 ^b	0	1	2	3	4	5	6	7	14	21	28 ^c	60	Unscheduled ^d
TB screening ^h	X													
Pregnancy test ⁱ	X													
Hematology (CBC + diff)	X				X					X				X
Coagulation (PT, PTT, INR)	X													
Chemistry (lytes, BUN, glucose, CR)	X				X					X				X
Liver profile (AST, ALT, Alb, AlkP, Tbili, Dbili)	X			X					X					X
Urinalysis	X													X
Adverse events	X	X	X	X	X	X	X	X	X	X	X	X		X
Concomitant medications ^l	X	X	X	X	X	X	X	X	X	X	X	X		X
Assessment for “off of oxygen” as defined for the primary endpoint ^o														
Assessment for “respiratory failure” as defined for the secondary endpoint														X
Assessment of survival (day of death if occurs) ^m	X											X	X	
Mavrilimumab/placebo administration		X												

^a Given resource limitation related to COVID-19, all laboratory testing is considered standard of care, though as possible, certain tests that are not considered standard of care may be obtained for research. If the laboratory tests in the schedule of activities are obtained, they will be documented accordingly. If laboratory tests cannot be obtained for other reasons, such as requiring extra use of personal protective equipment, unnecessary exposure to healthcare personnel, or safety issues related to obtaining and processing samples, these will not be considered a protocol deviation.

^b Study visits are planned for hospitalized patients only; planned activities that fall on study days that occur after the patient is discharged will not be done.

^c Screening activities can occur from -3 and 0 days before enrollment except for 2019-nCoV testing, which can occur between -7 and 0 days before enrollment.

^d For hospitalized patients, this visit will include the activities listed. For patients who have been discharged before Study Day 28, this visit will be conducted by phone/telehealth but will not include any laboratory tests.

^d An unscheduled visit is planned to occur on the day of discharge if the patient is discharged before Day 28; in which case this will serve as an early termination visit. If patient is discharged the visit on Study Day 28±3 and Study Day 60±3, will be done by telephone call follow-up and lab tests will not be performed. May also be used for adverse event assessments.

* Nasopharyngeal or oropharyngeal swabs for SARS-CoV2 RNA levels will be performed until negative or discharge. Sampling will include both nostrils, or repeat sampling will include the same nostril if only one nostril is used. A local sample will be used for inclusion criteria, and as possible appreciating the concerns related to extra use of personal protective equipment and exposure to healthcare personnel

"For the purposes of the primary end-point and time to freedom from supplemental oxygen, the ordinal scale and presence of supplemental oxygen will be assessed daily thru Day 14 while hospitalized. If patient has been discharged prior to Day 14, it will be assessed on Day 14, 21 and 28.

^e Collect at least baseline and at least weekly thereafter.

^g Includes FiO₂, SpO₂, Respiratory rate, note if ventilated or not, if yes collect PEEP; rescue therapy used (e.g., Flolan, proning, NM blockade, ECMO). For FiO₂, SpO₂, and PEEP, best and worst of daily value. Calculate P to F ratio best and worst for each day.

^h Done at Investigator's discretion; not expected to be used for decision to treat; not a mandatory test.

ⁱ Females of child-bearing potential only, urine or serum at investigator's discretion.

^j Includes complete blood count (CBC) and differential at screening and CBC on subsequent indicated days.

^l Prohibited medications include any cell-depleting biological therapies (e.g., anti-CD20) within 12 months prior to Day 0; or previous treatment with noncell-depleting biological therapies (such as anti-tumor necrosis factor [TNF], anakinra, anti-Interleukin [IL]-6 receptor [e.g. tocilizumab], or abatacept) within 8 weeks (or 5 half-lives, whichever is longer) prior to Screening, treatment with alkylating agents within 12 weeks prior to Screening, intramuscular, receipt of live (attenuated) vaccine within the 4 weeks before Day 0, treatment with cyclosporine A, azathioprine, cyclophosphamide, or mycophenolate mofetil (MMF) within 4 weeks of Screening. **Concomitant medications to track include: antipyretics, antibiotics related to secondary infections, and all investigational off-label therapies for COVID-19 for each subject (e.g. chloroquine, hydroxychloroquine, anti-IL-6, corticosteroids, remdesivir, lopinavir/ritonavir) along with time, dose, and duration of their administration.** Other concomitant medications will be recorded at baseline and daily thereafter while hospitalized until Day 7, at Day 14, Day 21 and Day 28. This information will be included in the final study report.

^o Assessed daily thru Day 14 if hospitalized. If the patient is discharged, assess at Day 14.

^m Document whether death occurred after withdrawal of care, and if so, reason for withdrawal of care.

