1.2 Purpose

The purpose of this prospective, proof-of-concept Phase 2, multicenter, blinded, randomized placebo controlled study is to demonstrate that early treatment with mavrilimumab prevents progression of respiratory failure in patients with severe COVID-19 pneumonia and clinical and biological features of hyper-inflammation. These results will lead to and inform a Phase III randomized placebo-controlled trial.

2 Objectives and endpoints

Primary Objective

To demonstrate that early treatment with mavrilimumab prevents progression of respiratory failure in patients with severe COVID-19 pneumonia and clinical and biological features of hyper-inflammation.

Secondary Objectives

- To evaluate mortality
- To evaluate the duration of hospitalization
- To evaluate safety of mavrilimumab

Primary Endpoint

The primary endpoint is the proportion of subjects alive and off of oxygen at day 14.

When hospitalized patients are off of oxygen, this will be documented as an oxygen saturation >90% for at least 5 minutes at rest. For patients that are discharged before day 14, a telehealth visit will be performed at day 14. For patients discharged **off** of oxygen before day 14, the day 14 visit will assess that they are off of oxygen. For patients who are discharged **on** oxygen before day 14, the decision to discontinue oxygen will be based on standard clinical care according to the health provider who prescribed oxygen therapy. The day 14 telehealth visit will assess whether the patient remains on oxygen, and “off of oxygen” will be defined as no supplemental oxygen use for at least the previous 24 hours.

Secondary Endpoints

The secondary end-points are alive at day 28, and the proportion of subjects alive and without respiratory failure at 28 days. Respiratory failure is defined as needing mechanical ventilation, non-invasive ventilation, or high-flow oxygen.

Exploratory Endpoints

- Mortality at day 14
- Mortality at day 60
- Proportion of patients in each category according to the following ordinal scale at day 7, 14, 21, and 28:
 1. Not hospitalized
 2. Hospitalized, no supplemental oxygen
 3. Hospitalized, on supplemental oxygen
 4. Hospitalized, requiring nasal high-flow oxygen or non-invasive ventilation
 5. Hospitalized, requiring ECMO, invasive mechanical ventilation or both
 6. Death
- Freedom from mechanical ventilation
- Duration of hospitalization
- Change in SOFA score at day 7, day 14, day 21, and day 28, or until discharge

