10.3 Analysis of the primary and secondary endpoints

Based on preliminary case-control data of patients with severe COVID-19 pneumonia treated with mavrilimumab, we estimate that 40% of patients in the placebo group will meet the primary endpoint compared to 80% of treated patients. A sample size of 30 patients per arm (60 total) will provide at least 80% power to detect this difference using a 2-sided alpha of 0.05.

The results of our study will inform treatment effect to aid in the planning of larger studies. The primary efficacy analysis will be on an intention-to-treat basis and include all patients who are randomized. Use of supplemental oxygen and vital status will be assessed daily up to day 14. Patients will be considered to have met the primary endpoint if the patient is alive at day 14 and has not used supplemental oxygen for at least 24 hours, regardless of whether or not the patient is still in the hospital (i.e. success=1). All other patients will be counted as not meeting the primary endpoint (i.e. success=0), including deaths on or before day 14 and patients for whom information cannot be ascertained (eg.lost to follow-up, withdrew consent, or otherwise missing information on the primary endpoint at day 14). This is analogous to imputing the worst case scenario for missing data.

The primary analysis will report the number and percentage of patients meeting the primary endpoint. The chi-square statistic will be used to test the difference between the two treatment groups. The time to freedom from supplemental oxygen will also be displayed geographically with a Kaplan Meier curve. A two-sided p value of < 0.049 will be considered statistically significant for the primary endpoint, though as noted, an important aspect of this study is to better define the magnitude of the treatment effect of our clinical outcomes to appropriately power larger studies.

The secondary endpoints are the proportion of patients alive at day 28 (i.e. success=1), and the proportion of patients alive and without respiratory failure at day 28 (i.e. success=1). Similar to the primary analysis, patients not meeting the this criteria in each of the secondary endpoints will be considered a failure (i.e. success=0), including deaths on or before day 28 and patients

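### The Table 7-1 notes conflict on follow-up after discharge, which puts the Day-14 primary endpoint status of discharged patients at risk

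*Combined protocol and SAP*

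**What the plan says.** For a patient discharged before Day 14, the protocol gives these instructions:

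- **Section 2, Primary Endpoint:** "For patients that are discharged before day 14, a telehealth visit will be performed at day 14". The section then says how oxygen status is judged for patients who left on oxygen and for those who left off it.
- **Table 7-1, general note:** visits are planned only for inpatients, and "planned activities that fall on study days that occur after the patient is discharged will not be done". No exception is stated.
- **Table 7-1, unscheduled-visit note:** a visit takes place on the day of discharge if that is before Day 28, "in which case this will serve as an early termination visit". It continues: "If patient is discharged the visit on Study Day 28±3 and Study Day 60±3, will be done by telephone call follow-up". Day 14 is not named.
- **Table 7-1, ordinal-scale and oxygen note:** "If patient has been discharged prior to Day 14, it will be assessed on Day 14, 21 and 28". This note refers expressly to the primary endpoint.
- **Table 7-1, note o, on the oxygen assessment:** "If the patient is discharged, assess at Day 14".

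Section 10.3 defines success as alive and off supplemental oxygen for at least 24 hours at Day 14, in hospital or not. The failure category includes patients lost to follow-up, withdrawn, "or otherwise missing information on the primary endpoint at day 14". Section 10.3 also plans a comparison once every patient has reached Day 14, has died, or has been discharged before Day 14.

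**The concern.** The instructions cannot all be followed. Section 7.1 tells sites to work from the assessment schedule, so its notes govern what is done at the bedside and after discharge. A site that follows the general note and the unscheduled-visit note would have no contact at Day 14 with a patient already at home.

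The missing-data rule then does the harm. A patient at home and off oxygen who is not called has no Day-14 status and is scored 0. Patients well enough to leave before Day 14 are likely to be mostly successes, so missed calls would fall mainly on successes. That lowers the observed rate in both arms, shrinks the absolute difference and costs power. The difference matters in its own right, because the trial is meant to size a later study.

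The analysis trigger adds to this. Read literally, a patient discharged on Day 5 already satisfies it, so the comparison could be run before that patient's Day-14 status is due. Status at discharge cannot stand in for it, least of all for a patient sent home on oxygen.

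A smaller consequence concerns the exploratory ordinal scale at Day 21. For a patient discharged before Day 14, one note requires it and another rules it out.

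**Working it through.** **Step 1. Compare the texts for a patient discharged before Day 14.**

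| Text | Contact after discharge |
|---|---|
| Section 2 | Day 14 (telehealth) |
| Table 7-1, general note | none |
| Table 7-1, unscheduled-visit note | Days 28 and 60 |
| Table 7-1, ordinal-scale and oxygen note | Days 14, 21 and 28 |
| Table 7-1, note o | Day 14 |

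Three of the five require Day 14, one rules out any contact, and one omits Day 14. The conflict is mainly between general and specific notes of the same table.

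**Step 2. Reproduce the stated power.** Inputs from Section 10.3: 30 per arm, 40% (placebo) against 80% (mavrilimumab), two-sided chi-square test, design alpha 0.05, significance threshold p < 0.049.

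Exact power is the sum of Bin(i; 30, 0.40) × Bin(j; 30, 0.80) over all 31 × 31 outcome pairs (i, j) whose uncorrected Pearson chi-square gives p below the threshold. The result is 90.5% at either threshold, or 85.1% with a continuity correction. Both support the plan's claim of at least 80%.

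**Step 3. Let a share m of true successes in each arm have no Day-14 contact.** They are scored 0, so the observed rates are

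p_placebo = 0.40 × (1 − m) and p_active = 0.80 × (1 − m),

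and the difference is 40 × (1 − m) points. Expected true successes are 30 × 0.40 = 12 and 30 × 0.80 = 24, so the expected numbers misscored are 12m and 24m. The value of m is an assumption, since the documents give none. Power is for the uncorrected test at p < 0.049.

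| m | Observed rates | Difference (points) | Misscored, placebo / active | Exact power |
|---|---|---|---|---|
| 0 | 40% v 80% | 40 | 0 / 0 | 90.5% |
| 5% | 38% v 76% | 38 | 0.6 / 1.2 | 86.5% |
| 10% | 36% v 72% | 36 | 1.2 / 2.4 | 82.1% |
| 12% | 35.2% v 70.4% | 35.2 | 1.4 / 2.9 | 80.3% |
| 20% | 32% v 64% | 32 | 2.4 / 4.8 | 72.0% |
| 30% | 28% v 56% | 28 | 3.6 / 7.2 | 60.4% |

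Power therefore reaches the stated 80% at about m = 12%.

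**Step 4. Convert this to missed calls.** If a share d of successes is discharged before Day 14, and a share u of those is not called, then m = d × u, so m = 12% needs u = 0.12 / d. The value of d is also not in the documents. For assumed values of 50%, 75% and 90%, u is 24%, 16% and 13%.

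**The case against.** The strongest reply is that the primary endpoint is already protected. Section 2 sets out the Day-14 telehealth procedure, and both table notes that deal with oxygen status require Day 14. Section 10.1 commits the investigators to every effort to document respiratory status and survival. To miss the call, a site would have to prefer a general sentence to three specific ones. The early-termination label is also weaker than it sounds: the same note goes on to schedule calls at Days 28 and 60, and Section 3 sets 60 days of follow-up per patient. The note's silence on Day 14 is an omission, not a prohibition.

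Most of this stands, and it limits the point. A reader might infer any of the following, none of which the documents support:

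- **That Table 7-1 ends all follow-up at discharge, or that the plan itself misscores discharged patients.** Only one note stops activity, and other notes to the table require later contact.
- **That power collapses because every site omits the call.** Nothing suggests that all sites would disregard Section 2 and the endpoint-specific notes.
- **That the estimate is biased against mavrilimumab through faster discharge in that arm.** The documents give no discharge rates by arm.
- **That the schedule fails to mark Day 14 in the off-oxygen row.** The row shows no marks in the extracted text, but the table is broken there, so nothing rests on it.

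What the reply does not remove is the contradiction. The general note has no exception, and the analysis trigger accepts discharge without a Day-14 status.

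**Conclusion.** The concern holds as an inconsistency among the Table 7-1 notes that bears on the primary endpoint. A discharged success is misscored only if a site follows the general note and makes no Day-14 contact, or if the analysis is run before that contact is due.

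The probability of this cannot be derived from the documents, so the figures show sensitivity and not an expected loss. The margin is modest: about 12% of true successes uncontacted in each arm, or roughly 3 active and 1 to 2 placebo patients, uses up the distance from 90.5% power to the stated 80%. This rests on the plan's own rates of 40% and 80%, an uncorrected chi-square test at p < 0.049, and equal proportional loss in the two arms. Under that equal loss, the error costs power and understates the absolute difference. It does not create false positives.

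The wording should be corrected, because the endpoint depends on it and the correction costs almost nothing.

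**What to change.** Amend the wording as follows:

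1. **General note to Table 7-1:** add an explicit exception, for example *remote contacts at Days 14, 21, 28 and 60 are still required after discharge*.
2. **Unscheduled-visit note:** add Days 14 and 21 to the telephone follow-up.
3. **Same note:** replace the early-termination label with *discharge visit; the patient remains in follow-up to Day 60*.
4. **Section 10.3, trigger for the Day-14 analysis:** require Day-14 oxygen and vital status for patients discharged earlier before the comparison is run.

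The cost is a set of wording changes in the next amendment. The Day-14 contact is already required by Section 2, so the only possible new work is a short Day-21 call at some sites. Item 4 may hold the Day-14 analysis until the last discharged patients reach Day 14, a wait of at most 14 days.
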